Title: Randomized Study on the Topical Application of Tranexamic Acid to the Wound Bed of Granulating Defects for Hemostasis in the Setting of Mohs Micrographic Surgery

NCT #: 04541303

Date: 20-MAY-2021

TITLE: Randomized study on the topical application of tranexamic acid to wound bed for hemostasis in the setting of Mohs micrographic surgery**1. ABSTRACT**

Mohs micrographic surgery (MMS) is considered the gold standard for treatment of high-risk non-melanoma skin cancer. Postoperative bleeding is a complication that can lead to further complications including necrosis, infections, take-down of repairs, patient distress and unnecessary return visits including possibly to emergency rooms after hours.

Tranexamic acid is an antifibrinolytic drug that prevents the breakdown of blood clots. The topical application of TXA has been shown to reduce intraoperative and postoperative bleeding in orthopedic, plastic, and maxillofacial surgeries. It has also been used topically as a hemostatic agent in anterior epistaxis and superficial oral trauma. This study aims to determine the efficacy of topical TXA in preventing postoperative bleeding when used as an adjunct to wound care on granulating defects in the setting of MMS.

2. OBJECTIVES

To perform a prospective randomized controlled trial to determine the hemostatic effect of TXA soaked gauze (intervention) versus normal saline soaked gauze (control) when applied to granulating defects in the setting of Mohs micrographic surgery by collecting the following data:

1. Rate of postoperative hemorrhagic complications.
2. Types of postoperative hemorrhagic complications.

3. BACKGROUND AND SIGNICANCE

Mohs micrographic surgery (MMS) is considered the gold standard for treatment of high-risk non-melanoma skin cancer.¹ Bleeding complication rates and severity are very low in cutaneous surgery,² but hematoma formation can lead to other complications such as infections, necrosis, and take-down of repairs such as grafts and flaps. The risk for bleeding complications is increased in some populations because anticoagulant and antiplatelet agents are typically not discontinued prior to Mohs surgery³. Intraoperatively, the modalities commonly used to decrease intraoperative and postoperative bleeding include the addition of adrenaline to local anesthetic, use of electrosurgery, suture ligation, and placement of topical hemostatic agents, such as absorbable hemostatic foam inserts.⁴ Postoperatively, pressure dressings are the standard preventative measure utilized in wound care to decrease risk of postoperative hemorrhage.⁵

Antifibrinolytics decrease bleeding by preventing the natural breakdown of formed blood clots. Several different pharmaceutical formulations are available, including tranexamic acid (TXA). TXA is a synthetic lysine analogue that blocks binding sites of plasminogen to lysine, thus preventing plasminogen activation to plasmin and the subsequent enzymatic lysis of polymerized fibrin in blood clots.⁶ TXA can be administered intravenously, orally, subcutaneously, or topically, for the reduction of bleeding.

Although only the oral form of TXA is FDA approved to reduce bleeding in women with heavy menstrual cycles,⁷ it is administered intravenously in a wide range of surgical specialties including cardiothoracic⁸, obstetric,⁹ orthopedic¹⁰, and trauma¹¹ to reduce risk of blood loss, and thus blood transfusions. Several studies have shown there is no increased risk of thrombotic events with this intervention⁶⁻⁹.

The topical application of TXA has been shown to reduce intraoperative and postoperative bleeding in cardiothoracic¹², orthopedic¹³, plastic¹⁴, and maxillofacial¹⁵ surgeries, as well as for anterior epistaxis.¹⁶ A recent meta-analysis of 71 RTCs, mostly in the setting of orthopedic surgery, showed that topical TXA can reduce the incidence of blood transfusions by 70%.¹⁷ Systemic absorption and cytotoxicity to *ex vivo* skin is negligible under concentrations of 25mg/ml.^{18,19} There is no increased risk of thromboembolic events or myocardial infarction when TXA is applied topically.¹⁷ To our knowledge, there has been no study in which topical TXA has been added to wound care in the setting of MMS with the aim to reduce postoperative bleeding.

4. STUDY PROCEDURES

A. Study design

- I. Prospective randomized controlled trial
- II. Location: University of Missouri Columbia Dermatologic Surgery Unit (Columbia, MO)
- III. Patients: All adult (18 years or older) patients presenting for Mohs micrographic surgery (MMS) for the treatment of melanoma or nonmelanoma skin cancer (NMSC) with a wound that will be healing by granulation
- IV. Patients meeting inclusion criteria will be randomized into two arms once enrolled in the study and will be randomized using computerized randomization software. The study personnel will randomize patients on the day of surgery.
 - a. One arm will serve as the control group and will receive normal saline soaked telfa pads to the wound bed upon completion of MMS.
 - b. A second arm will receive TXA 25mg/ml soaked telfa pads to wound bed upon completion of MMS. This concentration is based on studies showing possible decrease in re-epithelialization with chronic exposure to *in vitro* and *ex vivo* cutaneous wound bed models, as well as decreased viability of bovine and human cartilage, above this selected concentration.¹⁹⁻²¹
- V. Both solutions of the intervention and control are clear liquids that cannot be differentiated from one another. As such, the research staff will provide the surgeon with an unmarked sample cup of the either the saline solution or TXA solution, as selected by the randomization process for that individual patient. This will ensure that the surgeon, fellow, nursing staff, patient and family of patient are blinded to the intervention.

- VI. TXA will be provided by IDS and stored on-site/in-clinic in a temperature controlled and temperature monitored refrigerator. The volume of TXA solution needed for the intervention, see below, will be diluted to 25mg/ml by research staff and provided to surgeon once patient is enrolled.
- VII. Volume of both intervention and control substance will be determined by size of defect. All defects will be considered circles for the purposes of calculating wound area. The radius of the greatest dimension of the defect will be used to calculate the surface area using the formula, $A = \pi r^2$. A volume of 1ml per 1cm² will be dropped onto a Telfa pad that has been placed on the wound bed. A standard pressure dressing will be applied overtop.
- VIII. All patients will receive the same standardized post-operative wound care management instructions (see Appendix I)
- IX. Post-operative bleeding complications will be determined using the following data points (see Appendix II):
 - a. Did patient call with concern for post-operative bleeding on the same day of surgery, or post-operative day 0 (POD0)? YES/NO
 - b. Did patient call with concern for post-operative bleeding on POD1? YES/NO
 - c. Did patient call with concern for post-operative bleeding on POD2? YES/NO
 - d. Did patient return to clinic within post-operative days 0-2 for evaluation of post-operative bleeding complication? YES/ NO
 - e. Did patient receive postoperative intervention of any kind for hemorrhagic complication? YES/NO
 - f. Type of intervention performed for bleeding complication.
 - g. Perceived side-effects, if any, by patient due to study intervention.
- X. Study patients will be called 3 days after their surgical procedure to be asked the above data points in case a patient received outside care that was not disclosed to office or research staff.
- XI. Patients' medical charts will be reviewed for and patients will also be asked to divulge the following medical history for demographic and sub analysis purposes (see AppendixIII):
 - a. Age, sex, race
 - b. Medical history including hypertension, coronary vascular disease, liver disease, renal disease
 - c. Medications including anti-platelet agents and anti-coagulants

B. Study duration and number of study visits required of research participants.

- I. Duration sufficient to enroll 124 patients (62 per treatment arm). No additional patient visits will be required beyond the visit normally required for their procedure and/or suture removal.
- II. The initial visit for this study will take place after already scheduled Mohs micrographic surgery which will take no longer than one additional hour during the surgical visit.

- III. Participation includes a total of three days, specifically postoperative days 0-2.
- IV.
- C. Blinding, including justification for blinding or not blinding the trial, if applicable.
 - I. Double-blinded trial in which patients and surgeons will be masked to which treatment arm participants are assigned
- D. Justification of why participants will not receive routine care or will have current therapy stopped.
 - I. Care will be identical in both arms except for addition of topical application of TXA vs normal saline soaked gauze to wound bed at completion of MMS.
- E. Justification for inclusion of a placebo or non-treatment group.
 - I. There will be a control group of patients who do not receive the intervention, topical TXA, and instead will receive topical application of normal saline in order to provide a blinded comparison to the intervention arm. This will prevent unconscious bias from affecting patient and surgeon perception of postoperative bleeding complications.
- F. Definition of treatment failure or participant removal criteria.
 - I. Patient will be removed from the study if
 - i. Patient removes bandage and cleans wound within 24hrs
 - ii. Patient seeks postoperative care from outside institution within study timeframe (POD0-2), thus not allowing researchers to evaluate postoperative complication. This will be elucidated with a phone call three days after surgery.
 - II. Patients may also voluntarily leave the study. Only patients who complete all steps of the study will be included in data analysis, but the number of enrollees who do not complete the study will be tabulated to track if there is a significant difference between the groups.
- G. Description of what happens to participants receiving therapy when study ends or if a participant's participation in the study ends prematurely.
 - I. There will be no effect on the patient.

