7. STUDY STATISTICS

- A. Primary outcome variable.
 - I. Determination of effects of topical TXA on postoperative hemorrhagic complications and need for additional visits for care related to bleeding complications within the first 2 days following Mohs surgery with a wound allowed to heal by granulation
- B. Secondary outcome variables.
 - I. Determination of possible adverse effects, if any, that are different between the intervention and control arms.
- C. Statistical plan including sample size justification and interim data analysis
 - I. The statistical analysis will be performed by the University of Missouri biostatistics group. The sample size was calculated using a power analysis with the alpha set to 0.05 and the power set to 80%. Dichotomous variables were assessed with an anticipated change of bleeding of 10% in the intervention group and 30% in the control group based on prior clinical experience. No interim data analysis is planned.
 - II. Data will be analyzed on an intention to treat basis.
- D. Early stopping rules.
 - I. Study will end early if severe or high rate of adverse events occur.

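### The only visit item in the data points covers a return to clinic, which is narrower than the primary outcome and leaves some bleeding visits elsewhere with no place to be scored

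*Combined protocol and SAP*

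**What the plan says.** Section 7.A.I (primary outcome) covers hemorrhagic complications together with the "need for additional visits for care related to bleeding complications within the first 2 days following Mohs surgery". It sets no limit on the site of the visit. The abstract lists among the consequences of bleeding "unnecessary return visits including possibly to emergency rooms after hours".

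Section 4.A.IX states that bleeding complications are determined from a list of data points. Items a to c record a call about bleeding on POD0, POD1 and POD2. Item d is the only one about a visit: "Did patient return to clinic within post-operative days 0-2 for evaluation of post-operative bleeding complication". Item e asks "Did patient receive postoperative intervention of any kind for hemorrhagic complication", with no restriction on place and no stated window. Items f and g cover the type of intervention and perceived side effects.

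Section 4.A.X adds a telephone call three days after surgery, at which patients are "asked the above data points in case a patient received outside care that was not disclosed to office or research staff".

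Section 4.F.I.ii lists as a ground for removal: "Patient seeks postoperative care from outside institution within study timeframe (POD0-2), thus not allowing researchers to evaluate postoperative complication". Section 4.F.II adds: "Only patients who complete all steps of the study will be included in data analysis". Section 7.C.II, in contrast, specifies an intention-to-treat analysis.

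**The concern.** The outcome and the instrument do not match. The outcome counts bleeding visits wherever they occur; the item that should measure them counts one setting. A patient who bleeds when the clinic is closed may be seen somewhere else, and that is the kind of visit the abstract says the treatment should prevent.

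Two things are at stake. First, the visit component of the primary outcome is undercounted for each non-clinic visit scored by item d, even when another item shows that the patient bled. Second, a patient who was examined and reassured, without a prior call and without treatment, leaves no trace in items a to e. Such losses lower the observed event rates on which the sample size rests.

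**Working it through.** **Step 1. Follow a bleeding visit on POD0-2 through the written rules.**

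| Where the patient is seen | Item d | Other items | Removal rule (4.F.I.ii) |
|---|---|---|---|
| Study clinic | YES | a-c if the patient called, e if treated | Does not apply |
| Own institution's emergency or after-hours service | NO, read literally | a-c if the patient called, e if treated | Does not apply, since the care is not elsewhere |
| Another institution | NO, read literally | a-c if the patient called, e if treated | Patient removed; 4.F.II limits the analysis to completers |

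Row 2 is the clear gap. The visit itself is never scored, and the event is lost altogether if there was no call and no intervention. The documents name the site only as a university dermatologic surgery unit, so the existence of such a service is an assumption. In row 3 the result depends on which analysis rule governs: removal under 4.F, or a NO on item d if 7.C.II keeps the patient.

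**Step 2. Reproduce the planned sample size.** Inputs: 30% control and 10% TXA, alpha 0.05, power 80% (7.C.I); 62 per arm (4.B.I). Sidedness is not stated; two-sided is assumed. With pooled variance under the null and no continuity correction:

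n = [1.960 × √(2 × 0.20 × 0.80) + 0.842 × √(0.30 × 0.70 + 0.10 × 0.90)]² / 0.20²

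= (1.1087 + 0.4610)² / 0.04 = 61.6, so 62 per arm and 124 in total. This matches the plan.

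Power at 62 per arm = Φ[(0.20 × √62 − 1.1087) / 0.5477] = Φ(0.851) = 80.3%.

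**Step 3. Illustrate lost events.** Let f be the share of bleeding events seen only outside the clinic and caught by no other item. The documents do not give f. It is assumed equal in both arms, and the planned 30% and 10% are assumed to include these events. If they are recorded as no event, the rates become 0.30(1 − f) and 0.10(1 − f). For f = 20%:

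Φ[(0.16 × √62 − 1.960 × √(2 × 0.16 × 0.84)) / √(0.24 × 0.76 + 0.08 × 0.92)] = Φ[(1.2598 − 1.0162) / 0.5060] = Φ(0.482) = 68.5%.

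If the patients are removed instead, the expected arm sizes are 62(1 − 0.30f) and 62(1 − 0.10f), and the rates are 0.30(1 − f)/(1 − 0.30f) and 0.10(1 − f)/(1 − 0.10f). At f = 20% that leaves 58.3 controls and 60.8 TXA patients.

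| f | Recorded as no event: rates | Power | Patient removed: rates | Power |
|---|---|---|---|---|
| 0 | 30% vs 10% | 80.3% | 30% vs 10% | 80.3% |
| 10% | 27% vs 9% | 74.8% | 27.8% vs 9.1% | 76.6% |
| 20% | 24% vs 8% | 68.5% | 25.5% vs 8.2% | 72.3% |
| 30% | 21% vs 7% | 61.5% | 23.1% vs 7.2% | 67.3% |

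Both routes lose events and power. Removal also takes out more controls than TXA patients if the treatment works.

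**The case against.** A reader might infer that every emergency-department or other after-hours visit is recorded as no visit and that the day-3 call cannot recover it. The documents do not support that. For care at another institution, the written consequence is removal, not a NO. Sections 4.A.X and 4.F.I.ii both say that the call is there to find such care. What stands is narrower: the call may find the visit, but the listed items give no field in which to score it.

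The set of patients missed without being removed is also small by construction. They must attend the institution's own service, make no call on POD0-2 and receive no intervention; a treated bleed counts under item e wherever it was treated. Nothing in the documents suggests that this is common. The planned rates rest on clinical experience that is not described further, so it is unknown whether they include visits elsewhere and should be reduced at all. These points stand, and they limit the size of the problem. They do not remove the mismatch between item d and 7.A.I.

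One might also read the missing window in item e ("Did patient receive postoperative intervention of any kind for hemorrhagic complication") as letting a day-3 intervention count. Participation is limited to POD0-2 in 4.B.III and the outcome to the first two days in 7.A.I, so this is at most a point to clarify.

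Finally, Appendix II, the data form, was not in the text available for this review. It may hold a broader question or a location field. If so, 4.A.IX should be brought into line with it.

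**Conclusion.** The point holds in a limited form. Item d is narrower than the primary outcome and the stated rationale, and no listed item records a bleeding visit outside the clinic. The literal result is a NO on item d for a visit to the institution's own emergency or after-hours service. The same NO would arise for a visit elsewhere if intention to treat overrides the removal rule; otherwise that patient is dropped.

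The size cannot be determined from the documents. Power of 74.8%, 68.5% or 61.5% applies if 10%, 20% or 30% of events go unrecorded, equally in both arms, with no call or intervention to catch them and with planned rates that include them. Because items a to c and e catch patients who called or were treated, the true loss is probably smaller. The case for change rests on the outcome being only partly measured and on the low cost of correction, not on a demonstrated loss of power.

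**What to change.** 1. Reword item d in 4.A.IX, and in Appendix II if it has the same wording, to: *Did the patient have any unscheduled in-person visit for bleeding on POD0-2 (clinic, emergency department, urgent care or other provider)? YES/NO; where?*
2. Use the same wording in the day-3 call.
3. Reconcile this with 4.F.I.ii, 4.F.II and 7.C.II so that a bleeding visit at any site is recorded as an outcome and the patient stays in the analysis. Rewording item d alone does not count visits to other institutions while the removal rule stands.
4. As a minor clarification, add POD0-2 to item e.

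The cost is an edit to the data points, the form and the call script, plus an amendment to the removal and analysis-set text. No visits or patients are added. The drawback is that visits elsewhere rest on the patient's report, at a call that is already planned.

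### The secondary outcome compares adverse effects between arms, but the one adverse-effect item counts only effects that a blinded patient blames on the study product

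*Combined protocol and SAP*

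**What the plan says.** Section 7.B.I of the combined protocol and SAP gives one secondary outcome: "Determination of possible adverse effects, if any, that are different between the intervention and control arms".

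Section 4.A.IX lists seven data points, a to g. Items a to f concern bleeding: calls, return to clinic, and whether and how bleeding was treated. Item g is the only one on adverse effects: "Perceived side-effects, if any, by patient due to study intervention".

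On timing, section 4.B.III says "Participation includes a total of three days, specifically postoperative days 0-2", and section 4.A.X adds "Study patients will be called 3 days after their surgical procedure to be asked the above data points". On masking, section 4.C says "Double-blinded trial in which patients and surgeons will be masked to which treatment arm participants are assigned". No study visit is added (section 4.B.I).

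Two other places refer to harms without saying how they are found. Section 7.D would stop the study early for severe or frequent adverse events, and section 8.B.I sends problems and deviations to the IRB. The chart review in section 4.A.XI is for demographics, medical history and medications.

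**The concern.** The outcome and the item measure different things. The outcome is any adverse effect that differs between arms. A randomized comparison answers that without anyone judging cause: count all events in each arm and compare. Item g puts a causal judgement before the count, and gives it to the patient, who does not know the allocation and has a fresh surgical wound that can itself hurt, become irritated or become infected. An event blamed on the surgery is not an item g event, even if the product caused it.

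The likely result is few recorded events and a report of no difference in adverse effects. Readers could take that as evidence of tolerability when much of it may reflect how the question was worded.

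**Working it through.** **Step 1. Outcome and data side by side.**

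| Needed for 7.B | Provided in the supplied text |
|---|---|
| Adverse effects of any kind, by arm | Item g only; items a to f are about bleeding |
| Recorded regardless of presumed cause | Only if the patient perceives an effect and attributes it to the study product |
| The same prompts in both arms | No fixed list in the main text; Appendix II not supplied |
| A stated period | Days 0-2, with a call on day 3 |

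Sections 7.D and 8.B.I presuppose that events become known but add no way of collecting them.

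**Step 2. The plan's own figure.** Inputs from sections 7.C.I and 4.B.I: bleeding 30% versus 10%, alpha 0.05 (taken as two-sided; the plan does not say), power 80%, 62 per arm. With the pooled-variance formula and no continuity correction,

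n = [z₀.₉₇₅·√(2p̄(1−p̄)) + z₀.₈₀·√(p₁(1−p₁)+p₂(1−p₂))]² / (p₁−p₂)²

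and p̄ = 0.20: [1.960·√0.32 + 0.842·√0.30]² / 0.04 = (1.109 + 0.461)² / 0.04 = 61.6, rounded up to 62 per arm, 124 in total. The stated size reproduces. It was set for bleeding; the documents give no figure for adverse effects.

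**Step 3. What under-recording does.** Suppose a fraction s of true events is recorded, the same in both arms, with no false reports. Recorded rates are then s·p₁ and s·p₂, so the risk difference is multiplied by s. For n = 62,

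power = Φ{[|p₁−p₂|·√n − 1.960·√(2p̄(1−p̄))] / √(p₁(1−p₁)+p₂(1−p₂))}

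The true adverse-effect rates of 30% versus 10% below are an assumption. They are chosen because full recording then gives the plan's own 80%.

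| s | Recorded rates | Expected counts of 62 | Difference | Power |
|---|---|---|---|---|
| 1.00 | 30% v 10% | 18.6 v 6.2 | 20 points | 80% |
| 0.75 | 22.5% v 7.5% | 14.0 v 4.7 | 15 points | 65% |
| 0.50 | 15% v 5% | 9.3 v 3.1 | 10 points | 46% |
| 0.25 | 7.5% v 2.5% | 4.7 v 1.6 | 5 points | 25% |
| 0.10 | 3% v 1% | 1.9 v 0.6 | 2 points | 12% |

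For s = 0.50: (0.10·√62 − 1.960·√0.18)/√0.175 = (0.7874 − 0.8315)/0.4183 = −0.105, and Φ(−0.105) = 0.458. The approximation is rough in the lower rows. Exact enumeration with the uncorrected chi-square gives 81%, 47% and 23% for s = 1, 0.50 and 0.25, so the pattern does not depend on it.

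**Step 4. Zero reports in an arm.** The exact two-sided 95% upper bound for 0 of 62 is 1 − 0.025^(1/62) = 5.8% (one-sided 4.7%). That bounds the recorded rate. The bound on the true rate is 5.8%/s: 11.6% for s = 0.50 and 23.1% for s = 0.25 (from the unrounded 5.776%).

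**Step 5. What full recording would not buy.** With complete recording and 62 per arm, power is 18% for 5% versus 10%, 34% for 10% versus 20%, 46% for 5% versus 15% and 72% for 5% versus 20% (assumed rates). Better wording removes an avoidable loss. It does not make the trial sensitive to moderate harms.

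**The case against.** The strongest reply is that this is a short bleeding trial with short-term tolerability as its secondary outcome, and that a patient-reported item suits that aim. The one medical risk listed in section 8.A is a local allergic reaction, which a patient could notice and report. Masking makes under-reporting similar in both arms, so the comparison is not obviously biased. The unseen data form may prompt for specific symptoms.

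Most of this stands as a limit on the point. The problem is chiefly lost sensitivity rather than bias in favour of one arm. What does not stand is the fit between item and outcome: as worded, item g excludes events that 7.B covers.

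Three stronger readings are tempting, and the documents do not support them.

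- *That the trial fails to measure a healing harm it undertook to measure.* Section 4.A.IV.b does say "This concentration is based on studies showing possible decrease in re-epithelialization with chronic exposure to" laboratory wound models, but the sentence goes on to place the healing and cartilage signals above the concentration selected. It explains what the choice was meant to avoid; it does not predict harm. Section 7.B does not mention healing.
- *That item g is asked only once, on day 3.* Section 4.A.X presents the call as a safeguard against care not disclosed to the clinic. Nothing says item g cannot be recorded earlier.
- *That no adverse event could otherwise come to light.* Spontaneous reports are possible, and sections 7.D and 8.B.I assume some will be known. They simply give no collection method.

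**Conclusion.** The point holds in a limited form. The secondary outcome is a comparison of adverse effects, and the only item in the supplied text that feeds it is restricted to effects the masked patient attributes to the product. That lowers sensitivity and shrinks any true risk difference in proportion to the events missed. Under the assumed 30% versus 10%, recording half the events cuts power from 80% to 46%, and recording a quarter cuts it to 25%. The true rates and the recorded fraction are not in the documents, so these figures show the mechanism and do not forecast the result.

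Separately, observation through day 3 means that a finding of no difference could not support a statement about later healing in either direction. That limits interpretation; it is not a broken promise, and it does not mean harm is expected.

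The conclusion assumes that the main text gives the full content of item g, and that under-reporting is about equal in the two arms. If Appendix II already asks a fixed list regardless of attribution, only the wording of item g and 7.B needs aligning.

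**What to change.** 1. Reword item g and the matching entry on the data form. Ask every patient in both arms the same fixed list (local reaction, pain, infection, any other adverse event), and record each answer whether or not the patient attributes it to the study product. The patient's opinion on cause can be kept as a separate field, not as a condition for recording.
2. Restate 7.B as adverse effects reported through day 3, compared between arms, and say that no conclusion about wound healing will be drawn.

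The cost is a slightly longer call and an IRB wording update, with no new visit and no change in sample size. There is one statistical price: more ordinary surgical events will be recorded in both arms, and a higher background makes the same absolute difference harder to see. Step 5 shows it for a 10-point difference: 46% power at 5% versus 15%, but 34% at 10% versus 20%. Reporting each listed event separately, with counts and confidence intervals by arm, limits that dilution.

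A later chart review for healing is not needed to close this gap. It would go beyond the declared participation period, and its data would be incomplete and unstandardized.

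### The enrolment target of 124 equals the number that must be analysed for 80% power, with no margin for loss, and sections 4.F.II and 7.C.II disagree on who is analysed

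*Combined protocol and SAP*

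**What the plan says.** Four statements in the combined protocol and SAP bear on this point.

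- **Enrolment (4.B.I):** "Duration sufficient to enroll 124 patients (62 per treatment arm"). The figure counts patients enrolled, not patients analysed.
- **Justification (7.C.I):** "The sample size was calculated using a power analysis with the alpha set to 0.05 and the power set to 80" per cent. The effect is an "anticipated change of bleeding of 10% in the intervention group and 30% in the control group based on prior clinical experience". The section does not give the sidedness, the test or an allowance for loss.
- **Removal and analysis set (4.F):** Patients are removed for early removal of the bandage with cleaning of the wound, or for seeking care elsewhere during postoperative days 0–2. Voluntary withdrawal is allowed. Section 4.F.II then states: "Only patients who complete all steps of the study will be included in data analysis". Non-completers are to be counted and compared between the arms, but no rate is predicted.
- **Analysis principle (7.C.II):** "Data will be analyzed on an intention to treat basis".

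Section 4.A.X adds a telephone call three days after surgery. It asks every patient the bleeding questions, specifically to learn of care received elsewhere.

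**The concern.** A power calculation gives the number of patients who must contribute an outcome. When the same number is used as the enrolment target, each patient left out of the analysis lowers the power below the stated figure, unless the calculation had slack. Here the plan foresees exclusions and, in one of two conflicting sentences, says they will be left out.

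Two things are at stake. First, the 80% is the plan's only sample-size justification. Whether it holds depends on which sentence on the analysis set is followed and on a test that is not named. Both choices could be made after the data are seen.

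Second, the removal rule for outside care is tied to the outcome: a patient who goes elsewhere in the first days may be going because of bleeding. Dropping such patients can remove events as well as numbers. That is a matter of bias, and a larger sample would not cure it.

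**Working it through.** **Inputs.** Rates p₁ = 0.30 (saline) and p₂ = 0.10 (tranexamic acid), alpha 0.05 and power 80%, all from 7.C.I; 62 per arm from 4.B.I. Two-sidedness is inferred, because the one-sided formula gives 49 per arm (58 with continuity correction).

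**Step 1: reproduce the plan's figure.** With mean rate p̄ = 0.20,

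n per arm = [z₀.₉₇₅ √(2p̄(1−p̄)) + z₀.₈₀ √(p₁(1−p₁) + p₂(1−p₂))]² / (p₁−p₂)²

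= [1.960 × √0.32 + 0.8416 × √0.30]² / 0.04

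= [1.1087 + 0.4610]² / 0.04 = 2.464 / 0.04 = 61.6, so 62 per arm and 124 in total.

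This matches exactly. Other standard versions do not: unpooled variance gives 59, arcsine 60, and the continuity-corrected formula 71.2, so 72. The plan's number is thus consistent with an uncorrected two-sided test and contains no allowance for loss.

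**Step 2: power when fewer are analysed.** The normal approximation is Φ[(0.20√n − 1.1087) / 0.5477]. At n = 62 this is Φ[(1.5748 − 1.1087) / 0.5477] = Φ(0.851) = 80.3%.

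Exact power is the sum of Bin(x; n, 0.30) × Bin(y; n, 0.10) over all pairs (x, y) for which the test rejects at two-sided 0.05. The loss rates are assumptions, since the documents supply none.

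| Analysed per arm | Loss from 62 | Normal approximation | Exact, uncorrected chi-square | Exact, Fisher |
|---|---|---|---|---|
| 62 | none | 80.3% | 81.0% | 74.9% |
| 59 | about 5% | 78.2% | 80.5% | 72.0% |
| 56 | about 10% | 76.1% | 78.1% | 69.4% |
| 53 | about 15% | 73.7% | 75.5% | 67.7% |
| 50 | about 19% | 71.1% | 73.5% | 64.0% |

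**Step 3: effect of the unnamed test.** With all 124 analysed, the continuity-corrected chi-square has the same exact power as Fisher's test, 74.9%. By enumeration, Fisher's test reaches 79.97% at 68 per arm and 80.7% at 69, so it needs 69 per arm.

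**Step 4: is the uncorrected test suitable?** At the common rate of 20%, the expected counts per arm are 62 × 0.20 = 12.4 and 62 × 0.80 = 49.6, large enough for the Pearson chi-square.

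**Step 5: the two statements on the analysis set.** Under 7.C.II everyone randomised is analysed in the assigned arm, and only patients with no outcome at all reduce the 62. Under 4.F.II removed and withdrawn patients are left out even when their outcome is known. Both cannot govern the primary analysis.

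**The case against.** The sample-size arithmetic is right: 62 per arm reproduces exactly. Section 7.C.II commits to intention to treat, and if it governs and outcomes are obtained, removals cost no power. The design also keeps loss low, with follow-up over postoperative days 0–2, no extra visits and a call to every patient on day 3. With the test that matches the plan's number, exact power is still 80.5% at about 5% loss. All of this stands, and it rules out several stronger readings.

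- A reader might infer that the plan analyses completers only. It says so in 4.F.II and says otherwise in 7.C.II. The defect is the contradiction.
- A reader might infer that the trial fails to deliver 80% power. The documents do not support that. A shortfall needs 4.F.II to prevail with losses above about 5%, or a more conservative test. Losses of 15–20% are illustrations with no basis in the documents.
- A reader might treat Fisher's 74.9% as the trial's real power. The plan does not propose that test, and its own number points to an uncorrected one. The figure shows only what leaving the test open could cost.
- A reader might take the corrected formula's 72 per arm as Fisher's requirement. Enumeration gives 69.

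What remains is that the number has no margin, the test and sidedness are not stated, and the rule on who is analysed is contradictory.

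**Conclusion.** The point holds in conditional form. At 30% versus 10%, two-sided 0.05 and an uncorrected chi-square, 124 is the bare number to be analysed, and the plan makes it the number enrolled. If 4.F.II governs, 80% is kept only with an uncorrected test and about 5% loss or less. At an assumed 10% loss, power is 78.1% exact or 76.1% by normal approximation, a modest shortfall of about 2 to 4 points. If 7.C.II governs and every outcome is obtained, there is no shortfall with that test.

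Separately, removing patients who seek outside care may drop bleeding events and so bias the comparison. The documents do not allow the size of that effect to be estimated.

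**What to change.** 1. **Amend 4.F.II to agree with 7.C.II.** The primary analysis includes all randomised patients in their assigned arm. It uses the outcomes captured by the day-3 call (4.A.X), including bleeding treated at another institution. Keep the completers analysis as a sensitivity analysis. Editing 7.C alone would leave the contradiction in place.
2. **Name the test in 7.C.I:** the two-sided uncorrected Pearson chi-square.
3. **Restate the power in 7.C.I:** about 80% if all 124 patients contribute an outcome, and about 76–78% if 10% do not.

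The cost is a few sentences, with no added patients or visits. The stated power becomes slightly less favourable, and patients with no outcome at all still reduce the analysed number. Extra enrolment is not needed: 62 / 0.90 = 68.9, so 69 per arm, would offset a 10% loss, but it would neither resolve the contradiction nor recover bleeding events lost through removal.
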